10.3.3. Definition of Cardiovascular Events – Part B only

Cardiovascular Events (CV) Definition:

Investigators will be required to fill out the specific CV event page of the CRF for the following AEs and SAEs:

- Myocardial infarction/unstable angina
- Congestive heart failure
- Arrhythmias
- Valvulopathy
- Pulmonary hypertension
- Cerebrovascular events/stroke and transient ischemic attack
- Peripheral arterial thromboembolism
- Deep venous thrombosis/pulmonary embolism
- Revascularization

10.3.4. Recording and Follow-Up of AE and SAE

AE and SAE Recording

- When an AE/SAE occurs, it is the responsibility of the investigator to review all documentation (eg, hospital progress notes, laboratory, and diagnostics reports) related to the event.
- The investigator will then record all relevant AE/SAE information in the CRF.
- It is **not** acceptable for the investigator to send photocopies of the participant's medical records to GSK in lieu of completion of the GSK /AE/SAE CRF page.
- There may be instances when copies of medical records for certain cases are requested by GSK. In this case, all participant identifiers, with the exception of the participant number, will be redacted on the copies of the medical records before submission to GSK.
- The investigator will attempt to establish a diagnosis of the event based on signs, symptoms, and/or other clinical information. Whenever possible, the diagnosis (not the individual signs/symptoms) will be documented as the AE/SAE.

Assessment of Intensity

The investigator will make an assessment of intensity for each AE and SAE reported during the study and assign it to 1 of the following categories:

- Mild: An event that is easily tolerated by the participant, causing minimal discomfort and not interfering with everyday activities.
- Moderate: An event that causes sufficient discomfort and interferes with normal everyday activities.
- Severe: An event that prevents normal everyday activities. An AE that is assessed as severe should not be confused with an SAE. Severe is a category utilized for rating the intensity of an event; and both AE and SAE can be assessed as severe.

An event is defined as 'serious' when it meets at least 1 of the predefined outcomes as described in the definition of an SAE, NOT when it is rated as severe.

Assessment of Causality

- The investigator is obligated to assess the relationship between study intervention and each occurrence of each AE/SAE.
- A "reasonable possibility" of a relationship conveys that there are facts, evidence, and/or arguments to suggest a causal relationship, rather than a relationship cannot be ruled out.
- The investigator will use clinical judgment to determine the relationship.

- Alternative causes, such as underlying disease(s), concomitant therapy, and other risk factors, as well as the temporal relationship of the event to study intervention administration will be considered and investigated.
- The investigator will also consult the Investigator's Brochure (IB) and/or Product Information, for marketed products, in his/her assessment.
- For each AE/SAE, the investigator must document in the medical notes that he/she has reviewed the AE/SAE and has provided an assessment of causality.
- There may be situations in which an SAE has occurred and the investigator has minimal information to include in the initial report to GSK. However, it is very important that the investigator always make an assessment of causality for every event before the initial transmission of the SAE data to GSK.
- The investigator may change his/her opinion of causality in light of follow-up information and send an SAE follow-up report with the updated causality assessment.
- The causality assessment is one of the criteria used when determining regulatory reporting requirements.

Follow-up of AE and SAE

- The investigator is obligated to perform or arrange for the conduct of supplemental measurements and/or evaluations as medically indicated or as requested by GSK to elucidate the nature and/or causality of the AE or SAE as fully as possible. This may include additional laboratory tests or investigations, histopathological examinations, or consultation with other health care professionals.
- If a participant dies during participation in the study or during a recognized follow-up period, the investigator will provide GSK with a copy of any postmortem findings including histopathology.
- New or updated information will be recorded in the originally completed CRF.
- The investigator will submit any updated SAE data to GSK within 24 hours of receipt of the information.

10.3.5. Reporting of SAE to GSK

SAE Reporting to GSK via Electronic Data Collection Tool

- The primary mechanism for reporting SAE to GSK will be the electronic data collection tool.
- If the electronic system is unavailable, then the site will use the paper SAE data collection tool (see next section) in order to report the event within 24 hours.
- The site will enter the SAE data into the electronic system as soon as it becomes available.

- The investigator or medically-qualified sub-investigator must show evidence within the eCRF (e.g., check review box, signature, etc.) of review and verification of the relationship of each SAE to IP/study participation (causality) within 72 hours of SAE entry into the eCRF.
- After the study is completed at a given site, the electronic data collection tool will be taken off-line to prevent the entry of new data or changes to existing data.
- If a site receives a report of a new SAE from a study participant or receives updated data on a previously reported SAE after the electronic data collection tool has been taken off-line, then the site can report this information on a paper SAE form (see next section) or to the medical monitor by telephone.
- Contacts for SAE reporting can be found in the SRM

SAE Reporting to GSK via Paper CRF

- Facsimile transmission of the SAE paper CRF is the preferred method to transmit this information to the **medical monitor**.
- In rare circumstances and in the absence of facsimile equipment, notification by telephone is acceptable with a copy of the SAE data collection tool sent by overnight mail or courier service.
- Initial notification via telephone does not replace the need for the investigator to complete and sign the SAE CRF pages within the designated reporting time frames.
- Contacts for SAE reporting can be found in the SRM.

10.4. Appendix 4: Contraceptive Guidance and Collection of Pregnancy Information

10.4.1. Definitions:

Woman of Childbearing Potential (WOCBP) NB: WOCBP are not permitted to participate in the study

A woman is considered fertile following menarche and until becoming post-menopausal unless permanently sterile (see below).

If fertility is unclear (e.g., amenorrhea in adolescents or athletes) and a menstrual cycle cannot be confirmed before first dose of study intervention, additional evaluation should be considered.

Women in the following categories are not considered WOCBP

- Premenarchal
- Premenopausal female with 1 of the following:
 - Documented hysterectomy
 - Documented bilateral salpingectomy
 - Documented bilateral oophorectomy

For individuals with permanent infertility due to an alternate medical cause other than the above, (e.g., mullerian agenesis, androgen insensitivity), investigator discretion should be applied to determining study entry.

Note: Documentation can come from the site personnel's: review of the participant's medical records, medical examination, or medical history interview.

- Postmenopausal female
 - A postmenopausal state is defined as no menses for 12 months without an alternative medical cause.
 - A high follicle stimulating hormone (FSH) level in the postmenopausal range may be used to confirm a postmenopausal state in women not using hormonal contraception or hormonal replacement therapy (HRT). However, in the absence of 12 months of amenorrhea, confirmation with more than one FSH measurement is required.
 - Females on HRT and whose menopausal status is in doubt will be required to
 use one of the non-oestrogen hormonal highly effective contraception
 methods if they wish to continue their HRT during the study. Otherwise, they
 must discontinue HRT to allow confirmation of postmenopausal status before
 study enrolment.

Males must use the male condom and should be advised of the benefit for a female partner to use a highly effective method of contraception as outlined in Section 10.4.2.

10.4.2. Contraception guidance for female partners of males who are in the study^a:

[figure not shown]
- Highly Effective Methods^b That Have Low User Dependency
- Implantable progestogen-only hormone contraception associated with inhibition of ovulation^c
- Intrauterine device (IUD)
- Intrauterine hormone-releasing system (IUS)^c
- Bilateral tubal occlusion
- Vasectomized partner
 - Note: Vasectomized partner is a highly effective contraceptive method provided that the partner is the sole sexual partner of the woman of childbearing potential and the absence of sperm has been confirmed. If not, an additional highly effective method of contraception should be used. Spermatogenesis cycle is approximately 90 days.
- Highly Effective Methods^b That Are User Dependent
- Combined (estrogen- and progestogen-containing) hormonal contraception associated with inhibition of ovulation^c
 - oral
 - intravaginal
 - transdermal
 - iniectable
- Progestogen-only hormone contraception associated with inhibition of ovulation^c
 - oral
 - injectable
- Sexual abstinence
 - Note: Sexual abstinence is considered a highly effective method only if defined as
 refraining from heterosexual intercourse during the entire period of risk associated with
 the study intervention. The reliability of sexual abstinence needs to be evaluated in
 relation to the duration of the study and the preferred and usual lifestyle of the
 participant
- b. should be consistent with local regulations Failure rate of <1% per year when used consistently and correctly. Typical use failure rates differ from those when used consistently and correctly.
- c. Male condoms must be used and female partners of study male participants advised of the benefit to use hormonal contraception in addition If locally required, in accordance with Clinical Trial Facilitation Group (CTFG) guidelines, acceptable contraceptive methods are limited to those which inhibit ovulation as the primary mode of action.

Note: Periodic abstinence (calendar, sympto-thermal, post-ovulation methods), withdrawal (coitus interruptus), spermicides only, and lactational amenorrhoea method (LAM) are not acceptable methods of contraception for this study. Male condom and female condom should not be used together (due to risk of failure with friction)

10.4.3. Collection of Pregnancy Information:

Male participants with partners who become pregnant

- Investigator will attempt to collect pregnancy information on any male participant's female partner who becomes pregnant while participating in this study. This applies only to male participants who receive study intervention.
- After obtaining the necessary signed informed consent from the pregnant female partner directly, the investigator will record pregnancy information on the appropriate form and submit it to GSK within 24 hours of learning of the partner's pregnancy.
- The female partner will also be followed to determine the outcome of the pregnancy. Information on the status of the mother and child will be forwarded to GSK.
- Generally, follow-up will be no longer than 6 to 8 weeks following the estimated delivery date. Any termination of the pregnancy will be reported regardless of foetal status (presence or absence of anomalies) or indication for procedure.

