- 10. A history of insufficient pain relief from, or inability to tolerate, or contraindication to, oral NSAIDs.

11. Participant must be willing and able to understand and participate in all scheduled evaluations and to complete all required tests and procedures including the use of patient diaries. This will be judged by the Investigator during the screening period.

WEIGHT

12. BMI within the range 19-34.9 kg/m² (inclusive)

SEX

- 13. Male or female participant:
 - a. Male participants:

Male participants are eligible to participate if they agree to the following for at least 28 weeks after the dose of study intervention:

• Refrain from donating sperm

PLUS either:

• Be abstinent from heterosexual or homosexual intercourse as their preferred and usual lifestyle (abstinent on a long term and persistent basis) and agree to remain abstinent

or

- Must agree to use contraception/barrier as detailed below
 - o Agree to use a male condom
 - o and should also be advised of the benefit for a female partner to use a highly effective method of contraception (see Appendix 4) as a condom may break or leak when having sexual intercourse with a woman of childbearing potential who is not currently pregnant
- b. Female participants:

A female participant is eligible to participate if she is of non-reproductive potential as defined in Appendix 4.

INFORMED CONSENT

14. Capable of giving signed informed consent which includes compliance with the requirements and restrictions listed in the ICF and in this protocol.

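### In Part B, the HRT rule in Appendix 4 lets a woman of uncertain menopausal status enrol on contraception without confirmation, which undercuts the bar on women of childbearing potential (minor)

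*Protocol*

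**What the plan says.** - **Part B eligibility.** Protocol section 5.1, criterion 13b: "A female participant is eligible to participate if she is of non-reproductive potential as defined in Appendix 4". It contains no test of its own. Criterion 6 admits ages 40 to 75.
- **The bar.** Section 10.4.1 (Appendix 4): "WOCBP are not permitted to participate in the study". The same section treats a woman as fertile until she is postmenopausal, unless she is permanently sterile.
- **The HRT bullet.** This stands under the postmenopausal entry in the list of women who do not count as WOCBP. It begins "Females on HRT and whose menopausal status is in doubt will be required to" and goes on to require a highly effective non-oestrogen hormonal contraceptive if the woman wants to keep taking HRT. Otherwise she "must discontinue HRT to allow confirmation of postmenopausal status before" enrolment.
- **FSH.** A raised value is offered as confirmation only for women on neither hormonal contraception nor HRT. Also, "in the absence of 12 months of amenorrhea, confirmation with more than one FSH measurement is required". Section 1.3.1 schedules FSH and estradiol at screening; Table 4 of Appendix 2 makes them as-needed tests in women already classed as non-childbearing.
- **Reason for the restriction.** Section 4.3 limits the population to men and women of non-reproductive potential because reproductive toxicity data are lacking. The sentence sits in the paragraph on Part A but speaks of the study population, and criterion 13b applies the same limit to Part B.

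**The concern.** A woman whose menopausal status is in doubt has not been shown to be postmenopausal. Under the section's default rule she counts as fertile unless permanently sterile, and the bar would keep her out until the doubt is resolved. The HRT bullet gives her a way in that never resolves it. Contraception lowers the chance of pregnancy, but it does not establish non-reproductive potential, which is what criterion 13b asks for.

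At stake is exposure, over eight weekly 240 mg doses, of a woman whom the plan meant to exclude while reproductive toxicity is unstudied. There is also a consistency problem. Two sites could decide the same candidate differently, each citing Appendix 4, and the protocol allows no eligibility waivers.

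**Working it through.** The plan gives no figure on this point, so the check is a reading of the text followed by a rough sizing.

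**Step 1: does the bullet require confirmation?** It offers two alternatives joined by *otherwise*. Staying on HRT carries a contraception duty and no confirmation step. Stopping HRT carries the confirmation step. Confirmation therefore attaches to the second route only.

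**Step 2: is the first route open in Part B?** HRT is not among the Part B exclusions (section 5.2) or the prohibited medications (section 6.6). Section 6.5.1 lists antidepressants, nutraceuticals and low-dose aspirin as permitted for Part B and does not mention HRT. That list is not stated to be exclusive, and the bullet itself provides for HRT to continue during the study. In Part A, exclusion 18 and section 6.5.1 largely rule out other medication, so the point is confined to Part B.

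**Step 3: does anything else settle her status before dosing?**

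| Possible safeguard | Why it does not close the gap |
|---|---|
| Further evaluation when fertility is unclear (10.4.1) | Only to be considered, so optional; its examples are adolescents and athletes |
| Screening FSH and estradiol (1.3.1, Table 4) | FSH is not offered as confirmation while she takes HRT or a hormonal contraceptive, and on this route she takes both |
| Withdrawal for pregnancy (7.2) and 24-hour reporting (8.6.6) | Both act only once a pregnancy has occurred |
| Contraceptive methods (10.4.2) and pregnancy follow-up (10.4.3) | Both are written for female partners of male participants |

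**Step 4: how many women?** The documents give neither the share of women nor the share on HRT with doubtful status. Assume w = 60% women, and that a share h = 2% to 10% of them are affected. Then

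enrolled by this route = N × w × h; on active drug = half of that (1:1 randomisation, section 6.3.1).

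| N (section 4.2) | h = 2%: enrolled / active | h = 10%: enrolled / active |
|---|---|---|
| 20 (minimum) | 20 × 0.6 × 0.02 = 0.24 / 0.12 | 20 × 0.6 × 0.10 = 1.2 / 0.6 |
| 50 (planned) | 50 × 0.6 × 0.02 = 0.6 / 0.3 | 50 × 0.6 × 0.10 = 3.0 / 1.5 |
| 80 (maximum) | 80 × 0.6 × 0.02 = 0.96 / 0.48 | 80 × 0.6 × 0.10 = 4.8 / 2.4 |

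For the assumed shares these are upper figures, because some women would choose to stop HRT and be confirmed.

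**Step 5: expected pregnancies on active drug.** Footnote b of section 10.4.2 gives a failure rate under 1% per year with consistent and correct use. It is borrowed here from guidance meant for partners. Over Day 1 to Day 141, for the largest cell: 2.4 × 0.01 × 141/365 = 0.009.

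**The case against.** The strongest reply is that the bullet is a deliberate, specific rule. It sits inside the list of women who are not WOCBP, and criterion 13b takes in the whole appendix. On that reading a woman who follows the contraception route meets the definition and breaches nothing. This reading is possible, and it is why the point should not be put as a flat self-contradiction, which a reader might infer from setting the bar beside the bullet. It does not remove the difficulty, because an exception for women of unknown status defeats the stated purpose of the restriction. The method list and pregnancy follow-up were not extended to female participants either, which suggests leftover wording rather than a designed route.

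A second reply is that the bar and the 12-month amenorrhoea definition still govern. But the bullet is addressed to women whose status is in doubt, and it makes contraception the alternative to confirming it.

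A third reply is that stopping HRT for an eight-week treatment period is a burden, and that the route could be kept as a stated exception with a pregnancy test. That would remove the textual tension. It would still admit women of unconfirmed status without reproductive toxicity data, and would need its own method list and follow-up rules.

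The objection on size stands in full: the shares are assumed, and the effect is very small.

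A reader might also infer that no pregnancy testing is done. None appears in Table 4 or in the readable schedule rows, but some rows are redacted, so the documents do not show this and the point does not rest on it.

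**Conclusion.** The point holds as a minor, cheap improvement. In Part B the HRT bullet lets a woman on HRT with doubtful menopausal status enrol on contraception without confirmation, and nothing visible in the protocol closes that route. Few women are affected, possibly none: on the assumed shares, at most 0.6 to 3.0 at the planned size, and 0.24 to 4.8 over the permitted range of sizes. With correct contraceptive use, expected pregnancies on active drug stay below 0.01 even at the top of that range. Imperfect use would raise that figure; the documents give no rate for it.

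A reader might infer a serious safety failure or a threat to the trial's conclusions. The documents support neither. A pregnancy is not a likely event here, and randomisation, endpoints and analysis are untouched. The defect lies in an eligibility rule that does not do what it was written to do.

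**What to change.** Replace the HRT bullet in section 10.4.1 with wording such as:

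> A woman taking HRT whose menopausal status is uncertain, and who is not permanently sterile as described above, must stop HRT and have a postmenopausal state confirmed before she is enrolled. If this is not done, she is not eligible.

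Permanently sterile should cover documented hysterectomy, bilateral salpingectomy or bilateral oophorectomy, and any other permanent cause accepted under the existing rule that "investigator discretion should be applied to determining study entry". The change keeps the stop-and-confirm route already in the protocol, removes the unconfirmed one, and does not shut out permanently sterile women on HRT.

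The cost is one bullet in an appendix. FSH and estradiol are already in the screening schedule, and no endpoint or analysis changes. The downside falls on a few candidates, who must interrupt HRT to take part. The washout, whose length the protocol does not give, and repeat FSH where 12 months of amenorrhoea are lacking, must fit within the 42-day screening period or the one re-screen that section 5.4.1 generally allows. Some candidates will be delayed or lost.

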10.6. Appendix 6a: Liver Safety: Required Actions and Follow-up Assessments

Phase I liver chemistry stopping criteria have been designed to assure participant safety and to evaluate liver event etiology.

Phase I liver chemistry stopping criteria and required follow up assessments

t hase I liver enclinistry stopping effect a and required follow up assessments					
	Liver Chemistry Stopping Criteria – Liver Stopping Event				
ALT-absolute	ALT≥3xULN If ALT≥3xULN AND bilirubin ^{1,2} ≥ 2xULN (>35% direct bilirubin) OR INR				
	>1.5, Report as an SAE.		Assessments listed helpy		
	See additional Actions and Follow	Up F	ASSESSMENTS listed below		
	Required Actions and Follow	v up	Assessments		
	Actions		Follow Up Assessments		
	discontinue study intervention (Part	•	Viral hepatitis serology ³		
B only) Report the event to GSK within 24 hours		•	Obtain INR and recheck with each liver chemistry assessment until the transaminases values show		
	e liver event case report form omplete an SAE data collection		downward trend		
tool if the event also meets the criteria for an SAE ²		•	Obtain blood sample for pharmacokinetic (PK) analysis, as		
Perform liver chemistry event follow up assessments			soon as possible, and at least within 7 days ⁴		
Monitor the participant until liver chemistries resolve, stabilise, or return to within baseline (see MONITORING below)		•	Serum creatine phosphokinase (CPK) and lactate dehydrogenase (LDH).		
Do not restart or rechallenge participant with study intervention (Part B only)		•	Fractionate bilirubin, if total bilirubin≥2xULN		
MONITORING:		•	Obtain complete blood count with differential to assess eosinophilia		
If ALT≥3xULN AND bilirubin ≥ 2xULN or INR >1.5:		•	Record the appearance or worsening		
alkaline phos	chemistries (include ALT, AST, hypersensitivity, on the A report form (CRF)		of clinical symptoms of liver injury, or hypersensitivity, on the AE case report form (CRF)		
 Monitor participants twice weekly until liver chemistries resolve, stabilise or return to within baseline medications on the concor medications CRF page inc acetaminophen, herbal rer 		Record use of concomitant medications on the concomitant			
		medications CRF page including acetaminophen, herbal remedies, other over the counter medications.			

 A specialist or hepatology consultation is recommended

If ALT≥3xULN AND bilirubin < 2xULN and INR ≤1.5:

- Repeat liver chemistries (include ALT, AST, alkaline phosphatase, bilirubin) and perform liver event follow up assessments within 24-72 hrs
- Monitor participants weekly until liver chemistries resolve, stabilize or return to within baseline

 Record alcohol use on the liver event alcohol intake CRF page

[figure not shown]
If ALT≥3xULN AND bilirubin ≥ 2xULN or INR >1.5:

- Anti-nuclear antibody, anti-smooth muscle antibody, Type 1 anti-liver kidney microsomal antibodies, and quantitative total immunoglobulin G (IgG) or gamma globulins.
- Serum acetaminophen adduct high performance liquid chromatography (HPLC) assay (quantifies potential acetaminophen contribution to liver injury in participants with definite or likely acetaminophen use in the preceding week [James, 2009]).
 NOTE: not required in China
- Liver imaging (ultrasound, magnetic resonance, or computerised tomography) and /or liver biopsy to evaluate liver disease; complete Liver Imaging and/or Liver Biopsy CRF forms.
- Serum bilirubin fractionation should be performed if testing is available. If serum bilirubin fractionation is not immediately available, discontinue study intervention for that participant if ALT ≥ 3xULN and bilirubin ≥ 2xULN. Additionally, if serum bilirubin fractionation testing is unavailable, record presence of detectable urinary bilirubin on dipstick, indicating direct bilirubin elevations and suggesting liver injury.
- 2. All events of ALT ≥ 3xULN and bilirubin ≥ 2xULN (>35% direct bilirubin) or ALT ≥ 3xULN and INR>1.5, if INR measured, which may indicate severe liver injury (possible 'Hy's Law'), must be reported as an SAE (excluding studies of hepatic impairment or cirrhosis); INR measurement is not required and the threshold value stated will not apply to participants receiving anticoagulants.
- 3. Includes: Hepatitis A IgM antibody; Hepatitis B surface antigen (HbsAg) and Hepatitis B Core Antibody (IgM); Hepatitis CRNA; Cytomegalovirus IgM antibody; Epstein-Barr viral capsid antigen IgM antibody (or if unavailable, obtain heterophile antibody or monospot testing); Hepatitis E IgM antibody.
- 4. PK sample may not be required for participants known to be receiving placebo or non-GSK comparator interventions.) Record the date/time of the PK blood sample draw and the date/time of the last dose of study intervention prior to blood sample draw on the CRF. If the date or time of the last dose is unclear, provide the participant's best approximation. If the date/time of the last dose cannot be approximated, do not obtain a PK sample. If a liver event occurs following dose on Day 50 and a PK sample cannot be collected in the time period indicated above, a PK sample should be taken within 84 days post-dose. Instructions for sample handling and shipping are in the SRM

References

10.7. Appendix 6b: Healthy Volunteer and Patient Phase I Studies Liver Stopping Event Algorithm

Refer to Appendix 6a for required Liver Safety Actions and Follow up Assessments

